## **9. Ethical consideration**

### **9.1. The subject risks**

Blood samples collection will only bring minimal risk to the subjects. Only small volume of blood samples (~0.5 ml) will be drawn from the fingertip and using modern equipment which only cause small lesion on the incision site where the lancet or microtainer is introduced. A lancing device of the latest technology will be used to collect blood samples from the skin to collect sufficient blood volume with minimal pain. Blood sample collection will only be performed by trained staff of our investigator team to minimize the possibility of infection or other unlikely adverse events.

The risk of hemolysis in G6PD deficient subjects has been minimized by conducting G6PD screening to all schoolchildren and daily monitoring for hemolysis before and during PQ administration.

### **9.2. Benefit for study subjects**

All positive individuals will receive standard antimalarial treatment by the PHC staff. A G6PD screening and Hb measurement will be performed to maximize the safety of subjects receiving primaquine.

## **10. Expected application of results of the study**

The study is expected to provide an improved screen and treat strategy to clear hypnozoites by the use of highly sensitive detection tools. The reduction of hypnozoites in the liver will lower the reservoirs of *Plasmodium vivax* which hopefully will bring down the transmission.

Moreover, this study may offer a highly sensitive and practical diagnostic procedure that detects these carriers allows treatment, effectively empowering an efficacious approach to mass screen and treat (MSAT) interventions. The malaria research community engaged in discovery of targets of chemotherapy or immunoprevention would be offered a whole new universe of possibilities with sequestered gametocytes in the upper vasculature of the dermis.

## 11. Study Insurance

The research will be appropriately covered by the Oxford University's insurances.

## APPENDIXES

### APPENDIX A. MAP OF STUDY SITE

**APPENDIX B. DRUG DOSAGE****Table 1. DHA-PP**

DHA-PP will be given for any species. Same dosage will be given at the enrollment and during follow up.

Day	Drug	Daily dosage based on body weight						
		≤ 5 kg	6-10 kg	11-17 kg	18-30 kg	31-40 kg	41-59 kg	≥ 60 kg
1-3	DHA-PP	¼	½	1	1 ½	2	3	4

**Table 2. High dose Primaquine (PQ)**

Body weight (kg)	mg/tab	Tablet given/day	Actual dose given mg/kg BW	Total dose received (mg)
12	15	0,75	0,9375	6,5625
13	15	1	1,153846	8,076923
14	15	1	1,071429	7,5
15	15	1	1	7
16	15	1	0,9375	6,5625
17	15	1,25	1,102941	7,720588
18	15	1,25	1,041667	7,291667
19	15	1,25	0,986842	6,907895
20	15	1,5	1,125	7,875
21	15	1,5	1,071429	7,5
22	15	1,5	1,022727	7,159091
23	15	2	1,304348	9,130435
24	15	2	1,25	8,75
25	15	2	1,2	8,4
26	15	2	1,153846	8,076923
27	15	2	1,111111	7,777778
28	15	2	1,071429	7,5
29	15	2	1,034483	7,241379
30	15	2	1	7

31	15	2	0,967742	6,774194
32	15	2	0,9375	6,5625
33	15	2	0,909091	6,363636
34	15	2	0,882353	6,176471
35	15	3	1,285714	9
36	15	3	1,25	8,75
37	15	3	1,216216	8,513514
38	15	3	1,184211	8,289474
39	15	3	1,153846	8,076923
40	15	3	1,125	7,875
41	15	3	1,097561	7,682927
42	15	3	1,071429	7,5
43	15	3	1,046512	7,325581
44	15	3	1,022727	7,159091
45	15	3	1	7

**Table 3. Low dose Primaquine**

Single 0.25 mg/kg BW dose PQ will be given for *P. falciparum* or 14 days 0.25 mg/kg BW dose PQ for *P. vivax/P. ovale* infection any time during the study period.

Day	Species	Daily dosage based on body weight					
		≤ 5 kg	6-17 kg	18-30 kg	31-40 kg	41-59 kg	≥ 60 kg
1	P. falciparum	-	¼	½	¾	1	1
1-14	P. vivax/P. ovale	-	¼	½	¾	1	1

**Table 4 Quinine dose**

[figure not shown]
Day	Drug	Daily dosage based on body weight					
		≤ 5 kg	6-10 kg	11-17 kg	18-33 kg	34-40 kg	41-60 kg
1-7	Quinine	3 x 10 mg/kg BW	3 x ½	3 x 1	3 x 1½	3 x 2	3 x 2½

1 (1-14)	Primaquine	-	$\frac{1}{4}$	$\frac{1}{2}$	$\frac{3}{4}$	1	1
----------	------------	---	---------------	---------------	---------------	---	---

## APPENDIX C. TIME FRAME

[figure not shown]
Activity	2019								2020												2021										
	V	VI	VII	VIII	IX	X	XI	XII	I	II	III	IV	V	VI	VII	VIII	IX	X	XI	XII	I	II	III	IV	V	VI	VII	VIII	IX	X	
Protocol	x	x	x																												
Ethical review				x	x	x																									
Investigator meeting & trainings					x	x																									
Study approval						x	x																								
Site establishment						x	x																								
Socialization							x																								
Sero-positivity screening								x																							
School selection and randomization								x																							
Socialization, Informed Consent, and Training								x	x																						
Enrolment									x	x																					
Monthly sampling											x	x	x	x	x	x	x	x	x												
Family screening											x	x	x	x	x	x	x	x	x												
PCR & genotyping											x	x	x	x	x	x	x	x	x												
Data analysis																					x	x	x	x	x						
Publish findings																										x	x	x	x	x	x

## APPENDIX D. SAMPLE HANDLING WORKFLOW DURING INITIAL SCREENING

[figure not shown]
## APPENDIX E. MANAGEMENT OF ACUTE HEMOLYSIS

Any clinical concern of acute hemolysis (sign of anaemia e.g. breathless, fatigue, pale, dark urine, clinical jaundice) or falling haemoglobin during 7 days of treatment should trigger the following:

## APPENDIX F. MANAGEMENT OF METHEMOGLOBINEMIA

Any sign of metHb (dyspnea, headache, fatigue, weakness, dizziness, syncope) without sign of hemolysis should be followed by metHb measurement.

**APPENDIX G. PENETRATION DEPTH OF GENTEEL® LANCING DEVICE**

Contact Tip Color	Penetration Depth in mm
Blue	0.025
Yellow	0.66
Green	1.30
Clear	2.00
Orange	2.57
Violet	3.20

**APPENDIX I. RETREATMENT SCHEDULE ON ENROLMENT**

LMF	Antimalarial drugs	Pv Serology	
		Positive	Negative
Pf	3d DHP	7d PQ (1 mg/kgBW)	1d PQ (0.25 mg/kg BW)
Pv	3d DHP + 7d PQ	No further treatment	No further treatment
Pm	3d DHP	7d PQ (1 mg/kgBW)	No further treatment
Po	3d DHP + 7d PQ	No further treatment	No further treatment
Mixed Pf&Pv	3d DHP + 7d PQ	No further treatment	No further treatment
Mixed Pf&Pm	3d DHP	7d PQ (1 mg/kgBW)	1d PQ (0.25 mg/kg BW)
Mixed Pv&Pm	3d DHP + 7d PQ	No further treatment	No further treatment

**APPENDIX J. FORMS**

**CENSUS FORM**

**SEKOLAH :**

**KELAS :**

**TANGGAL :**

No	Nama	L/P	Tgl lahir / Usia	Nama Bapak	Nama Ibu	Desa	Dusun

**FORM SCREENING**

**SEKOLAH :** \_\_\_\_\_ **KELAS :** \_\_\_\_\_

**TANGGAL :** \_\_\_\_\_

No	ID	Nama	L/P	Usia	BB	Suhu	Demam seminggu terakhir	Serologi	Mikroskopik

**FORM FOLLOW UP**

**SEKOLAH :**

**ID :**

**KELAS:**

**USIA:**

**NAMA:**

**L/P**

Kohort	Tgl	BB	Suhu	Demam seminggu terakhir (Y/T)	LMF	LMS	qPCR
1							
2							
3							
4							
5							
6							
7							
8							
9							
Di luar jadwal							
Di luar jadwal							
Di luar jadwal							

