	
standard finger stick microscopic.
 
 
• In the SSAT arm at enrollment, only children who are Pv seropositive and/or LMF Pv/Po positive receive supervised high-dose primaquine (1mg/kg for 7 days) regardless of their symptoms. All blood slides will be processed and read directly after blood collection. Then treatment will follow if positive. Sero-positive children, on the other hand, will commence treatment after the result is available (approximately 1 week). Symptomatic or asymptomatic LMF positive for Pf/Pm will be treated according to current national guidelines.
 
• In the control arm at enrollment, only children who are symptomatic and LMF Pv/Po positive will receive supervised high-dose primaquine (1mg/kg for 7 days).
 
• In both arms at every other timepoint, symptomatic LMF positive children will receive treatment in accordance with national guidelines (unsupervised).
 
• In both arms at the final timepoint, LMF will be conducted on all children and if positive will be treated according to national guidelines.
 
• As blood schizontocides, DHA-PP for 3 days will be given according to body weight (national guidelines).
 

Inclusion and Exclusion Criteria
	
Inclusion:
 
 
• resident of study area and attending selected elementary school in Grade 1-5
 
• no evidence of health condition that would interfere with study participation
 
• assent of child and documented parental informed consent
 
 
Exclusion:
 
 
• G6PD deficiency as determined by SD Biosensor quantitative determination of <70% G6PD activity (male: <4 U/g Hb, female: <6 U/g Hb).
 
• Haemoglobin < 9 g/dL
 

Analysis plan and sample size calculation
	
The study is designed to show a superiority of SSAT vs. routine care for the prevention of recurrent P. vivax infections. The primary study endpoint will be the proportion of children with recurrent P. vivax by PCR during 9 months of follow-up. Secondary endpoints include time-to-first P. vivax recurrence as well as incidence of symptomatic

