### **5.2. Secondary objectives:**

1. To evaluate the performance of a point-of-care (POC) anti-*P. vivax* antibody detection test relative to Luminex (MagPix).
2. To evaluate safety of high dose PQ administration in schoolchildren.
3. To evaluate the accuracy of Sahli's method and Standard G6PD (SD Biosensor Inc., Deogyong-daero, Korea) relative to HemoCue for haemoglobin measurement.

4. To estimate the sensitivity and specificity of a microscopic diagnosis of blood by sample from skin (ankle) relative to standard finger stick microscopic and PCR.
5. To measure duration of gametocyte in the blood samples of the skin of the ankle and finger prick.
6. To estimate the sensitivity and specificity of magneto-optical hemozoin detection by Gazelle® (Hemex Health, USA) relative to standard finger stick microscopic and PCR. To analyse hemoglobinopathies in schoolchildren using HemeChip by Gazelle (Hemex Health, USA)

*Primary endpoint:* the proportional reduction of *P. vivax* incidence by PCR in children serologically screened relative to those receiving routine care during 9 months of active follow-up.

*Secondary endpoints:*

- (I) Difference in the time-to recur of *P. vivax* by PCR in SSAT and control arms.
- (II) Difference in the number of recurrent *P. vivax* by PCR in SSAT vs. control arms.
- (III) Difference in the incidence of recurrent symptomatic *P. vivax* by LMF in SSAT vs control arms.
- (IV) Seroconversion rate before and after intervention in SSAT and control arms.
- (V) Sensitivity and specificity of POC antibody detection test vs. gold standard Luminex assay.
- (VI) Adverse event (AE) and Severe Adverse Event (SAE) of high dose PQ in schoolchildren.
- (VII) Hb level in Sahli's method, Standard G6PD (SD Biosensor Inc., Deogyong-daero, Korea), and Gazelle® (Hemex Health, USA), in comparison with HemoCue (HemoCue AB, Angelholm, Sweden).
- (VIII) Sensitivity and specificity of microscopic examination to detect parasitemia from the shallow skin vasculature of the ankle (light microscopy-skin/LMS) compared to standard microscopic (light microscopy-finger/LMF) and PCR.

- (IX) Mean duration time of gametocyte in LMS and LMF
- (X) Sensitivity and specificity of magneto-optical hemozoin detection (MOD) compared to standard malaria detection and PCR.
- (XI) Sensitivity and specificity of Standard G6PD (SD Biosensor, Inc., Deogyong-daero, Korea Korea) compared to CareStart G6PD RDT (Access Bio. Inc., New Jersey, USA).

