### 6.3. Study design and study overview

The study design is a randomized controlled trial with serological screening and treatment as the intervention. Selected schoolchildren will be allocated into two study arms: (1) serological screening and treatment (SSAT), and (2) routine care as control arm.

At enrolment, in the SSAT arm, individuals found *P. vivax* positive by either serological (Luminex) or Giemsa stained microscopic examination regardless of the symptoms will receive supervised treatment (direct observation) with high dose PQ (daily 1 mg/kg BW) for 7 days ( $P_o=P_v$ ). In the control arm, only symptomatic individuals found *P. vivax* positive by Giemsa stained microscopic examination will receive the same regimen ( $P_o=P_v$ ). In addition, in the treated children of both arms, dihydroartemisinin-piperaquine (DHA-PP) will be given as blood schizontocide according to body weight. All other species (*P. falciparum*, *P. malariae*) found by Giemsa stained microscopic examination will be treated according to national guideline. Serological examination will be performed by Luminex (done at Eijkman, Jakarta) and point-of-care (POC) antibody detection using rapid test on site

Follow up will be performed monthly for 9 months. During this period, 400  $\mu$ L of finger pricked blood samples will be collected from all children in both arms. These samples will be tested for malaria presence by PCR which will be done at EO CRU, Jakarta. However, children with clinical symptoms (body temperature of  $\geq 37.5^\circ\text{C}$  and/or history of fever within 3 days), will be examined by Giemsa stained microscopy on site, and treated if positive (any species) according to national guideline (unsupervised).

At the last follow up, a mass blood survey will be conducted to both arms for *Pv* serological test, LMF, and PCR. Those found positive by LMF for any species will be treated regardless of their symptoms.

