### **6.7. Follow up and end of study**

First follow up will be conducted one month after the last dose of PQ treatment administration. Every visit, blood samples from finger prick and skin (LMS) will be taken. Unlike in the 16ecurrent process, malaria blood smear will be made only from participants with clinical symptoms suggestive for malaria. If positive, they will be treated. All treatment during follow up period will be provided by PHC staff according to national guideline (Appendix B table 1 & 3).

At the end of study (month-9 of the follow up), mass blood survey will be conducted to collect finger prick blood (LMF, Pv serological test, qPCR) and LMS. Seroconversion will be assessed. All LMF (+) will be treated as above.

All study subjects will be followed until the end of study (month 9) although they cannot fulfil the complete schedule.

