### 8.3. Data analysis

*Plasmodium vivax* incidence is defined as the total number of new genetically distinct *P. vivax* clones per child per detected during the follow up period. The analysis will use the comparison of two incidence rates between SSAT group and control group. For comparison, data will be entered as the number of recurrent *Pv* (numerators) and the total length of time people contributed in the cohort (person-time) as denominators. We will calculate the exact probabilities (Fisher's and Mid-P), the rate ratio with the exact confidence intervals and the measures of the impact of intervention. We will report the 95% of confidence interval for this comparison. Measures of the impact of intervention are computed for the prevented fractions in the exposed and in the population and the preventable fraction in the population.

As secondary endpoints, we will use Kaplan-Meier method to detect differences in the time-to-first recurrence of *Pv* by PCR in SSAT and control arms. The log-rank test is used to detect any difference between the two groups. Cox proportion hazard will be used to measure the effect size.

Multiple recurrences of *P. vivax* infections will be calculated during follow up. Number of events will be calculated, divided by the total length of time people

contributed in the cohort (person-time) as denominators. We will calculate the exact probabilities, rate ratio with the exact confidence intervals, and the measures of the impact of intervention using same tests as above.

Symptomatic recurrent *P. vivax* is defined as LMF positive with fever ( $\geq 37.5^{\circ}\text{C}$ ) or history of fever in the last 3 days during follow up. The same statistical test will be performed to compare both groups.

Difference of seropositivity between the two arms before and after the intervention will be calculated using chi-square test with p value  $< 0.05$  as limit of significance.

Sensitivity, specificity, positive predictive value, and negative predictive value of POC *Pv* antibody rapid test will be reported with Luminex as the golden standard.

Type and number of AE and SAE will recorded, and reported with total length of time people contributed in the cohort (person-time) as denominators.

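### The follow-up form records fever in the last week, but symptomatic *P. vivax* is defined by a 3-day history, so some smear-positive children cannot be reliably classified

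*Protocol*

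**What the plan says.** The text of the protocol uses a 3-day fever history throughout:

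- Section 5.2 lists, as secondary endpoint III, "Difference in the incidence of recurrent symptomatic" *P. vivax* by LMF between the arms.
- Section 8.3 defines such a case as LMF positive with a temperature of at least 37.5 °C "or history of fever in the last 3 days during follow up".
- Section 6.3 sets the follow-up microscopy trigger: children at or above 37.5 °C and/or with a "history of fever within 3 days), will be examined by Giemsa stained microscopy on site".
- Section 6.6 lists the 3-day fever history among the items to be recorded at enrolment.
- The lay summary in the Synopsis gives the same 3 days for routine-care treatment at enrolment.

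The forms in Appendix J use a different window. The follow-up form has the column "Demam seminggu terakhir (Y/T" (fever in the last week, yes/no), next to columns for temperature (Suhu) and LMF. Its three unscheduled-visit rows share these columns. The screening form has "Demam seminggu terakhir", with no yes/no coding printed. The family form repeats the weekly item. The case report form has no fever-history item. Section 8.1 says only that fever history is recorded, without a window.

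On who is smeared, section 6.7 says that during follow-up "malaria blood smear will be made only from participants with clinical symptoms suggestive for malaria". For the final timepoint, the Synopsis says that "LMF will be conducted on all children and if positive will be treated according to national guidelines". Appendix H marks LMF at enrolment and in every follow-up month, with no symptom restriction.

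**The concern.** A yes to fever in the last week covers fever 1 to 3 days ago and fever 4 to 7 days ago alike. Without an onset date the two cannot be separated afterwards, and no analysis plan can recover a date that was not collected. Endpoint III needs that separation for any smear-positive child who is not febrile at the visit.

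The same item stands on the screening form. At enrolment all children are smeared, and in the control arm symptomatic status separates the LMF *P. vivax*/*P. ovale*-positive children who receive supervised primaquine from those who do not. If the form holds only a weekly answer, adherence to the written 3-day rule cannot be checked from it.

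**Working it through.** No figure in the plan is at stake, so the check sets the recorded fields against the definition.

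**Step 1. Rule (section 8.3).** Symptomatic = LMF positive AND (temperature ≥ 37.5 °C OR fever in the last 3 days).

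**Step 2. Fields available (follow-up form).** Temperature, fever in the last week (yes/no) and LMF result.

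**Step 3. Every combination for an LMF-positive child.**

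| Temperature | Fever in last week | Endpoint III |
|---|---|---|
| ≥ 37.5 °C | yes | met |
| ≥ 37.5 °C | no | met |
| < 37.5 °C | no | not met (no fever in 7 days implies none in 3) |
| < 37.5 °C | yes | undetermined (days 1–3 or only days 4–7) |

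Three of the four combinations are settled and one is not.

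**Step 4. When the undetermined combination arises.**

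- *Months 1 to 8, smears limited by the section 6.3 rule.* The existence of an LMF result implies that the temperature or 3-day criterion was met, so the combination is largely resolved.
- *Months 1 to 8, looser readings.* Section 6.7 speaks only of symptoms suggestive of malaria, which weakens that inference. If LMF is done at every visit, as Appendix H marks it, the inference fails. The follow-up form has no field for why a smear was made.
- *Month 9.* All children are smeared, so an LMF result says nothing about symptoms and the combination cannot be resolved.

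Of the nine monthly visits, the text thus leaves one clearly exposed (month 9). Read literally, Appendix H exposes all nine.

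**Step 5. Direction.** Every fever in the last 3 days is also a fever in the last 7. Treating the weekly yes as symptomatic therefore gives a count at least as large as the true 3-day count. Treating every undetermined child as not symptomatic gives a count no larger than it. The gap between the two is the number of undetermined children, and the documents give nothing from which to predict that number.

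**Step 6. Enrolment.** Section 6.6 says the 3-day history is recorded; the screening form offers only the weekly item. The text and the form disagree, and no other form in Appendix J supplies the missing item.

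**The case against.** The strongest reply is that the data settle most cases. Temperature has its own column, a no for the week answers the 3-day question, and the section 6.3 rule makes a smear in months 1 to 8 evidence that the criterion was met. Section 7.1.1 supports this, since it has only the 400 µL sample taken in those months. This stands and limits the point. A reader might infer from the mismatch that endpoint III cannot be derived at all; the table above shows that this is wrong. What the reply leaves open is month 9, and any earlier visit at which smears are not limited by the 3-day rule.

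A reader might also infer that field staff will use the weekly answer to decide who is smeared or, among controls at enrolment, who is treated. No section makes the form item the trigger. Sections 6.3 and 6.6 and the lay summary all state 3 days. What the documents show is a gap in documentation; a 7-day rule in practice would be conjecture.

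A third tempting step is to put a size on the excess. Suppose, as an assumption, that fevers start at a constant rate and last d days. A 7-day recall then catches (6 + d)/(2 + d) times as many as a 3-day recall: 7/3 = 2.3 for d = 1, 9/5 = 1.8 for d = 3 and 11/7 = 1.6 for d = 5. These ratios concern fever histories among all children. They do not measure inflation of endpoint III, which depends on smear-positive children without measured fever, and the documents give no fever durations.

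Finally, the screening and family forms do not supply endpoint III, which is counted during follow-up in trial participants. The screening form matters only for the enrolment status described above. No 3-day rule is stated for household members, so the family form is left out of the point.

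**Conclusion.** The mismatch is real and stands in the protocol's own text and forms. LMF-positive children without measured fever who answer yes to fever in the last week cannot be reliably classified for secondary endpoint III. This holds at month 9, and at earlier visits to the extent that LMF is not limited by the 3-day rule. Use of the weekly answer can only add cases. The size of the excess cannot be computed from the documents, and they give no basis for saying which way the rate ratio between the arms would move.

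Separately, the screening form does not document the 3-day status that section 6.6 says is recorded and on which control-arm treatment at enrolment depends.

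A reader might infer that the primary endpoint is compromised. The documents do not support that: PCR detection does not use the fever item, and an effect through wrongly treated controls would require the field practice that no section describes. The point is therefore a form-versus-text inconsistency affecting one secondary endpoint and one enrolment record. It is worth correcting because the lost information cannot be recovered once the visits have taken place.

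**What to change.** Before enrolment, replace the weekly fever item on the follow-up and screening forms with days since last fever (0 to 7, or none). This supports either window. Then reconcile the forms with sections 6.3, 6.6 and 8.3 and the lay summary so that one window is stated everywhere; which window applies is for the sponsor to confirm. The LMF row of Appendix H should be reconciled with sections 6.3 and 6.7 at the same time, because it decides how many visits are exposed.

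The cost is one field on two forms. If visits have already been recorded on the present form, report endpoint III twice, with the undetermined children counted first as symptomatic and then as not, and give their number by arm. This shows the uncertainty but does not remove it.

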## 6.6. Enrolment

During enrolment, finger pricked blood samples will be collected from all participants. At this activity, body temperature will be recorded using infrared thermometers, body weight will be scaled, history of fever within 3 days and taking antimalarial drugs within last 2 weeks will be recorded. Finger pricked blood samples will be made into malaria blood smear and tested by POC Pv antibody rapid detection. A total of 400  $\mu$ L will be collected into microtainer tube containing EDTA to be sent to field laboratory, and separated for various tests, e.g. serology (Luminex), PCR, Hb, G6PD, and Hemex.

All participants' blood samples will be tested for the presence of antibodies to a validated panel of *P. vivax* antigens (using a gold-standard laboratory test) at the Eijkman Institute for Molecular Biology, Jakarta. Blood samples will be shipped every 2 days, and the result will be reported to the field team within no more than 1 week.

On site, blood slides will be Giemsa stained (see 7.3) and assessed by microscopy with 1000x magnification. Screening for G6PD deficiency will be performed quantitatively by Standard G6PD (SD Biosensor, ROK) with the cut off of 4 U/g Hb (male) or 6 U/g Hb (female) on the same day of blood collection. Hb level will be measured using HemoCue and Hb Sahli. Other substudies (LMS, hemozoin detection, hemoglobinopathy) will also be conducted (see 6.10)

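### On the forms shown, follow-up fever history covers the last week, but secondary endpoint III needs the last 3 days, so some slide-positive children cannot be classified as defined

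*Protocol*

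**What the plan says.** Secondary endpoint III in Protocol section 5.2 is worded "Difference in the incidence of recurrent symptomatic" *P. vivax* by finger-prick light microscopy (LMF), SSAT against control. Section 8.3 defines a symptomatic recurrence as a positive slide with a temperature of at least 37.5 °C or "history of fever in the last 3 days during follow up".

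The same window governs who gets a smear during follow-up. Under section 6.3, children with a raised temperature and/or "history of fever within 3 days), will be examined by Giemsa stained microscopy on site". Section 6.7 confirms that at follow-up visits a "malaria blood smear will be made only from participants with clinical symptoms suggestive for malaria". Month 9 differs: "At the end of study (month-9 of the follow up), mass blood survey will be conducted to collect finger prick blood", including LMF, from all children.

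At enrolment, section 6.6 says that "history of fever within 3 days and taking antimalarial drugs within last 2 weeks will be recorded". The lay summary in the synopsis applies a 3-day symptom history to the treatment of routine-care children.

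The forms in Appendix J use another window. The follow-up form asks "Demam seminggu terakhir (Y/T" (fever in the last week, yes or no), and the screening form has "Demam seminggu terakhir". Neither asks for a date of last fever. Both have a temperature column (*Suhu*). Section 8.1 sends fever history to the case report forms without naming a window, but the case report form shown has no fever item.

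**The concern.** Fever in the last week and fever in the last 3 days are different facts, and the first does not determine the second. If the week answer is all that is collected, endpoint III cannot be derived as defined for a recognisable group of slide-positive children. Counting them all includes some whose fever ended too early. Counting none of them drops some true events. An analysis plan could choose between these conventions, but it could not recover a 3-day history that was never asked for.

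The screening form raises a separate matter. It does not feed endpoint III, which counts events during follow-up. Its one-week item cannot document the 3-day history that section 6.6 promises. Nor can it show that the symptom rule for treating slide-positive control children at enrolment was applied as written.

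**Working it through.** The plan states no figure for this point, so there is none to reproduce. The check sets the definition against the form fields.

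**Step 1. Cross-classify *P. vivax* slide-positive children at follow-up.**

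| Temperature at visit | Fever in last week (form) | Status under section 8.3 |
|---|---|---|
| ≥37.5 °C | yes or no | symptomatic |
| <37.5 °C | no | not symptomatic (none in 7 days means none in 3) |
| <37.5 °C | yes | undetermined: a last fever within 3 days qualifies, 4 to 7 days back does not |

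Only the third row is affected.

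**Step 2. Find the visits at which the third row occurs.** At months 1 to 8, sections 6.3, 6.7 and 7.1.1 confine smears to symptomatic children. If staff apply the 3-day rule, the existence of a smear implies that the criterion was met. The form cannot confirm this, because it asks about the week. At month 9 every child is smeared whatever the symptoms, so the smear carries no information on fever and the third row is open.

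**Step 3. Illustrate the scale.** The documents give no data on fever timing, so the share of undetermined children outside the 3-day rule could be anything from 0 to 100%. Assume that the last fever day is evenly spread and that slide positivity is unrelated to it.

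- Last fever 1 to 7 days before the visit: days 4, 5, 6 and 7 fall outside, so 4/7 = 57%.
- Also allow a child who was febrile earlier on the visit day but afebrile when measured (days 0 to 7): 4/8 = 50%.

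**Step 4. Screening form.** Section 6.6 promises a 3-day history; the form holds a one-week item. For a control child who is slide-positive, afebrile and positive for the week, the form cannot show whether treatment was due under section 6.3 read with the 3-day history in the synopsis lay summary.

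**The case against.** The strongest objection is that Appendix J is plainly not the whole data-capture set. Section 6.9 names an SAE form that is not there. Section 6.6 requires recent antimalarial use to be recorded, and no form shown has a field for it. The screening form has no field for HemoCue, Sahli, hemozoin or hemoglobinopathy results. The sheets may be outline field logs, with the 3-day item collected elsewhere. This stands as a limit on the claim: a reader might infer that the trial cannot derive endpoint III, but the documents support only that the forms shown cannot. It does not remove the mismatch, since wherever the text gives a window it is 3 days and wherever a form asks about fever history it is a week.

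A reader might also infer a percentage error in endpoint III. With visits every 28 days, fever lasting *d* days and no episode seen outside schedule, qualifying visit-days number 9(3 + *d*), and counting every week-yes child at month 9 adds 4. The excess is 4/40 = 10% for *d* = 1 and 4/76 = 5% for *d* = 5. But fever length is not in the documents, and the follow-up form has three rows for unscheduled visits. If a share *p* of episodes is seen at those visits, the excess is 4(1 − *p*)/[252*p* + (1 − *p*)(31 + 9*d*)]. This is 3/93 = 3% at *p* = 0.25, *d* = 1, and 2/164 = 1% at *p* = 0.5, *d* = 5. A biased rate ratio is also tempting, but a constant effect gives no shift, and any shift needs an assumed effect that fades by month 9. None of these figures is a finding.

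Appendix H ticks LMF at every monthly visit without a symptom limit. If that row were followed, the undetermined group would extend beyond month 9. Whether it should be followed is a separate conflict over the smear schedule and is not part of this point.

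Finally, the consequence is small. No month-9 treatment turns on the fever answer, because all slide-positive children are treated then. That stands.

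**Conclusion.** The mismatch holds, and it is minor. On the forms shown, a slide-positive child who is afebrile and positive for fever in the last week cannot be classified under section 8.3. The gap lies mainly at month 9, and at months 1 to 8 the form cannot verify the smear rule. The screening form has the same item, which affects documentation of the enrolment history and of the control-arm treatment rule, not endpoint III.

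The reach is one secondary endpoint. Both arms use the same form, and the primary endpoint rests on PCR at every visit without reference to fever. The number of children affected is unknown from the documents. The figure of about half outside the 3-day rule rests on evenly spread fever timing and on slide positivity that does not depend on it. Confidence is high in the mismatch and lower in its consequence, because other forms may exist.

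**What to change.** On the follow-up and screening forms, replace the one-week item with two fields: fever in the last 3 days (yes/no) and days since last fever. The first matches the section 8.3 definition and the section 6.3 trigger; the second allows the answer to be checked. If a form outside Appendix J already captures the 3-day history, cite it in section 8.1 and bring the Appendix J forms into line.

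The cost is two fields on each form before enrolment, with no extra children, visits or procedures. It has to be done before data collection, since these forms would not allow the history to be rebuilt afterwards.
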